1. for MCM, end of first trimester
2. for all other outcomes, end of pregnancy

or occurrence of the outcome of interest (whichever comes first).

Exposure information will be derived from outpatient visits and/or prescription data, as recorded in the data source for each country. Country-specific cohorts of eligible women or

woman/offspring units will be identified, depending on the outcome of interest. A summary of the study design is presented in [Table 3](#).

Table 3: Summary of study design

Topic	Outcome	Population	Inclusion assessment window	Exposure assessment period	Index date	Follow-up	
						Offspring	Mother
Congenital anomalies	MCM	Live and non-live offspring	min 12 months prior to LMP2	from LMP2 to end of first trimester of pregnancy ¹	LMP2	from LMP2 to max 1y of age	NA
Select pregnancy loss outcomes	Composite of spontaneous abortion and stillbirth	All pregnancies	min 12 months prior to LMP2	from LMP2 to end of pregnancy ¹	LMP2	NA	end of pregnancy
Congenital anomalies	mCM	Live and non-live offspring	min 12 months prior to LMP2	from LMP2 to end of pregnancy ¹	LMP2	from LMP2 to max 1y of age	NA
Adverse pregnancy outcomes	Ectopic pregnancy	All pregnancies	min 12 months prior to LMP2	from LMP2 to end of pregnancy ¹	LMP2	NA	end of pregnancy
Adverse pregnancy outcomes	Spontaneous abortion	All pregnancies	min 12 months prior to LMP2	from LMP2 to end of pregnancy ¹	LMP2	NA	end of pregnancy
Adverse pregnancy outcomes	Elective termination of pregnancy	All pregnancies	min 12 months prior to LMP2	from LMP2 to end of pregnancy ¹	LMP2	NA	end of pregnancy
Adverse pregnancy outcomes	Stillbirth	All pregnancies	min 12 months prior to LMP2	from LMP2 to end of pregnancy ¹	LMP2	NA	end of pregnancy
Adverse pregnancy outcomes	Composite of foetal loss	All pregnancies	min 12 months prior to LMP2	from LMP2 to end of pregnancy ¹	LMP2	NA	end of pregnancy
Adverse pregnancy outcomes	Infections requiring hospitalisation during pregnancy	All pregnancies	min 12 months prior to LMP2	from LMP2 to end of pregnancy ¹	LMP2	NA	end of pregnancy
Adverse pregnancy outcomes	Emergency caesarean section	All pregnancies	min 12 months prior to LMP2	from LMP2 to end of pregnancy ¹	LMP2	NA	end of pregnancy
Adverse birth outcomes	Preterm birth	Live offspring	min 12 months prior to LMP2	from LMP2 to end of pregnancy	birth	NA	NA
Adverse birth outcomes	Small for gestational age	Live offspring	min 12 months prior to LMP2	from LMP2 to end of pregnancy	birth	NA	NA

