
Secondary objective 5c-d, 8 & 9
 
Exploratory objective 13 & 14
	
pregnancy outcomes, separately and as a composite of foetal loss
 
Estimate relative risk of select pregnancy loss outcomes (composite of spontaneous abortion and stillbirth), adverse pregnancy outcomes, separately and as a composite of foetal loss.
 
Describe cohort demographic and clinical characteristics.
 
Among pregnant women
			
 Ectopic pregnancies (except for ectopic pregnancy outcome)

Primary objective 3 & 4
 
Secondary objective 5c-d, 8 & 9
 
Exploratory objective 13 & 14
	
Describe and estimate risk of select pregnancy loss outcomes (composite of spontaneous abortion and stillbirth), adverse pregnancy outcomes, separately and as a composite of foetal loss.
 
Estimate relative risk of select pregnancy loss outcomes (composite of spontaneous abortion and stillbirth), adverse pregnancy outcomes, separately and as a composite of foetal loss.
 
Describe cohort demographic and clinical characteristics.
 
Among pregnant women
	
Unexposed study population
	
pregnancy_unexp
	
EXCLUSION:
 
 Pregnancies exposed at any time to anifrolumab (+16 weeks prior to LMP2) (see Section 9.3.1) Ectopic pregnancies (except for ectopic pregnancy outcome)

Secondary cohort birth (birth_exp+ birth_unexp)
				

Secondary objective 5c-d, 10 & 11
	
Describe and estimate risk of adverse birth outcomes.
 
Estimate relative risk of adverse birth outcomes.
 
Describe cohort demographic and clinical characteristics.
 
Among live offspring
	
Exposed study population
	
birth_exp
	
INCLUSION:
 
 Pregnancies exposed at any time to anifrolumab (+16 weeks prior to LMP2) Pregnancies with linkage mother-offspring within the study time period

Objective	Main features	Input Cohort/ Population	Sub-cohort Abbreviation	Additional criteria to be applied to the input Cohort/ Population

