- **Spontaneous abortions**¹²: unintended loss of an intrauterine pregnancy which is less than 22 weeks of gestation for the European data sources (40); less than 20 weeks for the USA data sources (64);
- **Ectopic pregnancy:** occurs when a fertilised egg implants outside of the uterus, usually in one of the fallopian tubes.
- **Elective termination of pregnancy:** is defined as the intentional termination of pregnancy at any time in gestation for any reason. When possible, reasons for elective termination are captured and classified as elective termination of pregnancy for foetal anomaly or for other reasons.
- **Stillbirth**¹³: unintended foetal death occurring at or after 22 weeks of gestation for the European data sources (78); at or after 20 weeks for the USA data sources (64).
- **Composite of foetal loss:** will be defined as the presence of at least one of the following: spontaneous abortion, ectopic pregnancy, elective termination of pregnancy and stillbirth.
- **Infections requiring hospitalisation during pregnancy:** infections requiring hospitalisation during pregnancy will be considered as the occurrence of the first event of a hospitalisation for an infection diagnosis, as primary diagnosis. The list of the infections considered, and their respective ICD-10 codes are presented in [Table 24](#).
- **Emergency caesarean section:** surgical procedure involving the incision of the walls of the abdomen and uterus for delivery of an offspring that occurs when vaginal delivery is

¹⁴ Specific outcome censoring rules will be applied. For spontaneous abortion and ectopic pregnancy there will be outcome specific end of follow-up dates. For spontaneous abortion outcome specific end of follow-up will be 22 weeks of gestation as for the ectopic pregnancy end of follow-up will be 16 weeks of gestation further details will be specified in the SAP.

¹⁵ To maximize the capture of non-live births for spontaneous abortion, elective termination, and stillbirth, an exhaustive list of codes related to pregnancies as well as to outcomes will be used, i.e., every code will be included.

discontinued due to unexcepted complications during labour, such as the occurrence of foetal distress (105).

Adverse birth outcomes

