To estimate the relative risk of mCM in live and non-live offspring from the mothers who had moderate/severe SLE and were exposed or unexposed to anifrolumab during pregnancy (study objective 7), the crude and adjusted RRs (with corresponding 95% CI) will be estimated using the *mCM* cohort. The crude RR and its 95% CI will be estimated using a regression model as specified in Section [9.7.1](#). The adjusted RR and its 95% CI will be estimated using the same regression model following an appropriate PS adjustment method as described in Section [9.7.1](#).

Objective 8

The analysis to describe and estimate the risk of adverse pregnancy outcomes (as defined in Section [9.3.2](#)) in all pregnancies from the mothers who had moderate/severe SLE and were exposed or unexposed to anifrolumab during pregnancy (study objective 8) will be performed using the *pregnancy* cohort (as defined in Section [9.2.2](#)). The crude and adjusted cumulative incidence (with corresponding 95% CI) of the adverse pregnancy outcomes (as defined in Section [9.3.2](#)) will be calculated for cases where the mother was exposed to anifrolumab during pregnancy and for cases where the mother was unexposed to anifrolumab during pregnancy. The crude cumulative incidence (i.e., risk) will be calculated as the total number of each adverse pregnancy outcome (as defined in Section [9.3.2](#)) divided by the total number of pregnancies. The adjusted cumulative incidence (i.e., risk) will be estimated following PS adjustment.

Objective 9

To estimate the relative risk of adverse pregnancy outcomes (as defined in Section 9.3.2) in pregnancies from the mothers who had moderate/severe SLE and were exposed or unexposed to anifrolumab during pregnancy (study objective 9), the crude and adjusted RR (with corresponding 95% CI) will be estimated using the *pregnancy* cohort (as defined in Section 9.2.2). The crude RR and its 95% CI will be estimated using a regression model as specified in Section 9.7.1. The adjusted RR and its 95% CI will be estimated using the same regression model following an appropriate PS adjustment method as described in Section 9.7.1.

Objective 10

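### Emergency caesarean section is analysed per pregnancy rather than per delivery, so its risk ratio mixes caesarean risk with differences in miscarriage and termination

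*Protocol*

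**What the plan says.** Section 9.3.2 describes the outcome as a "surgical procedure involving the incision of the walls of the abdomen and uterus for delivery of an offspring", performed when complications in labour stop a vaginal delivery. By that definition a pregnancy has to reach delivery to be at risk.

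The analysis text does not carry this through:

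- Table 3 (section 9.1) has the row "Emergency caesarean section All pregnancies".
- Section 9.7.3, Objective 8, covers the adverse pregnancy outcomes "in all pregnancies from the mothers who had moderate/severe SLE and were exposed or unexposed to anifrolumab during pregnancy (study objective 8"), using the pregnancy cohort. The crude risk "will be calculated as the total number of each adverse pregnancy outcome", "divided by the total number of pregnancies".
- Objective 9 estimates crude and adjusted RRs in the same pregnancy cohort.
- Section 9.7.1 makes the risk measure an incidence proportion, so a pregnancy that ends early stays in the denominator as a non-event.

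Table 5 (section 9.2.2) makes one relevant restriction to the pregnancy cohort: "Ectopic pregnancies (except for ectopic pregnancy outcome"). The line stands under an exclusion heading for the unexposed sub-cohort. For the exposed sub-cohort no such heading shows in the text at hand, which may be an artefact of reading the table.

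No text restricts emergency caesarean section to deliveries. By contrast, Objectives 10 and 11 analyse preterm birth and small for gestational age in live offspring.

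**The concern.** A pregnancy that miscarries or is terminated cannot have an emergency caesarean, yet it is scored in the favourable category. The per-pregnancy risk is therefore the product of two quantities: the probability of reaching delivery and the caesarean risk once there. Any group difference in the first passes straight into the RR.

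This matters here because pregnancy loss is the study's own safety question. It is a primary outcome, and section 7.4 cites a non-significant excess of embryo-foetal loss in exposed monkeys. The caesarean RR is tied arithmetically to that outcome and moves against it. Propensity score adjustment does not remove the link, because the Table 7 covariates are measured before or at conception or the start of exposure, whereas loss comes afterwards. The limitations in section 9.9 do not mention the effect on this outcome.

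At stake is whether a caesarean RR below 1 could be reported as reassuring, or a modest harm missed, when the difference comes from pregnancies that never reached delivery.

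**Working it through.** The protocol gives no rate, sample size or power for emergency caesarean section, so there is no stated figure to reproduce.

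**Inputs**

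- Spontaneous abortion in the comparator group, A = 16%, with a bracketed range of 12.1% to 19.9% (section 9.5.1.1).
- Abortion RR of 1.5, 2.0 and 2.5. The last equals the protocol's non-inferiority margin; all three are scenarios, not forecasts.
- Terminations, T: no rate is given. Taken as 0, then as an assumed 15% in both groups.
- Ectopics are left out, as Table 5 requires. Stillbirths are counted as deliveries with the same caesarean risk as live births (an assumption).

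**Formula.** Let q0 and q1 be the caesarean risks per delivery in comparator and exposed pregnancies. Then

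apparent RR = (q1/q0) × (1 − A × RR_abortion − T) / (1 − A − T).

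The level of q cancels, so no caesarean rate is needed.

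**No effect per delivery (q1 = q0), T = 0**

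| Abortion RR | A = 16% | A = 12.1% | A = 19.9% |
|---|---|---|---|
| 1.5 | 0.76/0.84 = 0.90 | 0.8185/0.879 = 0.93 | 0.7015/0.801 = 0.88 |
| 2.0 | 0.68/0.84 = 0.81 | 0.758/0.879 = 0.86 | 0.602/0.801 = 0.75 |
| 2.5 | 0.60/0.84 = 0.71 | 0.6975/0.879 = 0.79 | 0.5025/0.801 = 0.63 |

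At an abortion RR of 1 with equal terminations, every entry is 1.00.

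**Equal terminations, T = 15%, A = 16%.** 0.61/0.69 = 0.88, 0.53/0.69 = 0.77 and 0.45/0.69 = 0.65. Terminations that are equal in both groups create no distortion of their own, but they enlarge one that is already present.

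**When a true increase is reversed (A = 16%, T = 0).** The apparent RR falls below 1 only if q1/q0 is less than 0.84/0.76 = 1.11, 0.84/0.68 = 1.24 or 0.84/0.60 = 1.40 at the three abortion RRs. A true 20% increase per delivery would show as 1.2 × 0.76/0.84 = 1.09, 1.2 × 0.68/0.84 = 0.97 and 1.2 × 0.60/0.84 = 0.86.

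**Absolute risk.** In the comparator group with T = 0, the per-pregnancy risk is 0.84 × q0, which is 16% below the per-delivery risk. Terminations widen the gap.

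**The case against.** The strongest counter-argument is that risk per pregnancy from conception is a legitimate measure. It captures the total effect of exposure and keeps the cohort fixed at the index date, where confounders are measured. Restricting to deliveries conditions on a post-exposure event that the drug may affect, which brings its own selection exactly when loss differs. This stands. It argues for adding a per-delivery estimate rather than substituting one, but the protocol neither states nor justifies the total-effect choice.

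Second, spontaneous abortion, termination and stillbirth are reported by exposure group in the same cohort, so a reader could largely rebuild a crude per-delivery risk. Also, an abortion RR of 2.5 would be a major signal that nobody would overlook. This is partly right. Small-number masking (section 9.7) can block the reconstruction, it yields no adjusted RR, and the distortion is already about 10% at an abortion RR of 1.5.

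Four stronger readings are tempting but are not supported:

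- *Ectopic pregnancies dilute the outcome too.* Table 5 keeps them only for the ectopic outcome. Read as an inclusion for the exposed sub-cohort, the line's exception clause would make no sense.
- *The full 20% loss composite drops out*, giving 0.70/0.80 = 0.88, 0.60/0.80 = 0.75 and 0.50/0.80 = 0.63. That composite contains stillbirths, which are deliveries; the 16% for spontaneous abortion is the matching input.
- *A drug that raises loss will appear to lower caesareans.* This holds only if the per-delivery risk is unchanged or rises by less than the thresholds above. A larger rise is attenuated, not reversed.
- *Exposed pregnancies will be terminated more often because most are unplanned.* Section 9.5.1.1 expects most exposed pregnancies to be unplanned but says nothing about termination. A difference between groups is an assumption.

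The distortion can also run the other way. Section 9.9 accepts that shorter pregnancies are more likely to fall in the unexposed cohort, which would push the per-pregnancy caesarean RR upwards.

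**Conclusion.** The point holds in a conditional form. The protocol fixes both the population and the denominator for emergency caesarean section, so this is not a detail left for the analysis plan, and the denominator includes pregnancies that cannot have the event. With 16% spontaneous abortion, no terminations and no effect per delivery, the apparent RR is about 0.90, 0.81 or 0.71 at abortion RRs of 1.5, 2.0 or 2.5. If neither abortion nor termination differs between groups, the RR is undistorted and only the absolute risk is affected: about 16% below the per-delivery risk before terminations, whose rate the protocol does not give.

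The figures assume that stillbirths carry the same caesarean risk as live births. They are crude and illustrative, not predictions of what anifrolumab does.

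The scope is one secondary outcome. It has no power claim, it lies outside the meta-analysis (which covers the primary objectives only), and no primary result changes. The change should be made because it alters what this outcome can conclude.

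**What to change.** - In Table 3, Table 5 and Objectives 8 and 9, add the risk and RR of emergency caesarean section among pregnancies ending in live birth or stillbirth, using the protocol's own stillbirth limits (at or after 22 weeks in the European sources, 20 weeks in the USA).
- Show the proportion of each exposure group that reaches delivery beside it.
- If the per-pregnancy risk and RR are kept, label them as a total-effect measure with pregnancy loss and termination as competing events.
- Check that the ectopic line for the exposed sub-cohort in Table 5 carries its exclusion heading in the source document.

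The cost is protocol wording and one subset filter, with the propensity score and RR models run once more in that subset; no new data are needed. The downside is that the per-delivery estimate conditions on a post-exposure event and must be read together with the loss results, as the preterm and small-for-gestational-age analyses in live births already must be.

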9.7.4 Exploratory objectives

The analysis for the exploratory study objectives will be conducted separately for each data source. The description of the analysis to be conducted for each exploratory study objective is provided in the following sections.

Objective 12

The analysis to describe and estimate the risk of adverse outcome related to infant growth up to one year of age in live offspring from the mothers who had moderate/severe SLE and were exposed or unexposed to anifrolumab during pregnancy (study objective 12) will be performed using the

infant cohort (as defined in Section 9.2.2). The crude and adjusted cumulative incidence (with corresponding 95% CI) of adverse outcome related to infant growth will be calculated for cases where mother was exposed to anifrolumab during pregnancy and for cases where mother was unexposed to anifrolumab during pregnancy. The crude cumulative incidence (i.e., risk) will be calculated as the total number of adverse outcomes related to infant growth divided by the total number of live offspring. The adjusted cumulative incidence (i.e., risk) will be estimated following PS adjustment.

Objective 13

To describe and estimate the risk of select pregnancy loss outcomes (composite of spontaneous abortion and stillbirth) in pregnancies occurring in women with moderate/severe SLE who were exposed or unexposed to anifrolumab in specific pregnancy trimesters (study objective 13), the pregnancy trimester specific exposure groups where the exposure to the study or comparator treatment is during a specific pregnancy trimester (trimester 1 only; trimester 1&2 only; trimester 2&3 only; trimester 3 only; all trimester 1&2&3) will be generated from the *pregnancy* cohort (as defined in Section 9.2.2). The analysis for the pregnancy trimester specific exposure groups will be performed separately by comparing each exposed group and its comparator group as shown in Table 6 in Section 9.3.1. This requires that the PS adjustment is done separately for 5 exposure group comparisons i.e., 5 different PS models will be fitted on each of the exposure group comparisons separately. Also, the crude and adjusted cumulative incidence will be calculated separately for each of the 5 exposure group comparisons (as shown in Table 6 in Section 9.3.1) to estimate the risk of the select pregnancy loss outcomes in pregnancies occurring in women with moderate/severe SLE with pregnancy trimester specific exposure to the anifrolumab. The crude cumulative incidence (i.e., risk) will be calculated as the total number of select pregnancy loss outcomes (composite of spontaneous abortion and stillbirth) divided by the total number of pregnancies in pregnancy trimester specific study cohorts. The adjusted cumulative incidence (i.e., risk) will be estimated following PS adjustment.

Objective 14

To estimate the relative risk of select pregnancy loss outcomes (composite of spontaneous abortion and stillbirth) in pregnancies occurring in women with moderate/severe SLE and who were exposed anifrolumab in specific pregnancy trimester (study objective 14), the crude and adjusted RRs (with corresponding 95% CI) will be estimated separately for each specific pregnancy trimester exposure groups as defined in Section 9.7.1. The crude RR will be estimated separately for each pregnancy trimester specific exposure groups using a regression model as specified in Section 9.7.1. The adjusted RR will be estimated using the same regression model following an appropriate PS adjustment method as described in Section 9.7.1.

Objective 15

The analysis to describe and estimate the risk of MCM by target body system organ class in live and non-live offspring from the mothers who had moderate/severe SLE and were exposed or unexposed to anifrolumab during the first trimester of pregnancy (study objective 15) will be performed using the *MCM* cohort (as defined in Section 9.2.2). The crude and adjusted cumulative incidence (with corresponding 95% CI) of the MCM by target body system organ class in live and non-live offspring from the mothers will be estimated separately for cases where mother was exposed to anifrolumab during the first trimester of pregnancy and for cases where mother was unexposed to anifrolumab during the first trimester of pregnancy. The crude cumulative incidence (i.e., risk) of MCM by target body system organ class will be calculated as the total number of live and non-live offspring with MCM divided by the total number of live and non-live offspring per each target body system organ class. The adjusted cumulative incidence (i.e., risk) will be estimated following PS adjustment.

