For the adverse birth outcomes, the **index date**, included in the enrolment, will be defined as the delivery/birth date from which the offspring will be followed up for the outcome of interest. The **exit date/end of follow-up** will be defined as the end of the study period, death, emigration (where available), loss to follow-up (disenrollment/de-registering), or 1 day after delivery/birth, whichever is the soonest. The list of the adverse birth outcomes and their respective ICD-10 codes are presented in [Table 25](#).

- **Preterm birth:** defined as live births less than 37 weeks of gestation (<37 weeks)
- **SGA:** is defined as a birth weight lower than the 10th percentile of the distribution of birth weights among live births, by gestational age and sex, using a validated global reference for foetal weight and birthweight (76).

Exploratory outcomes

For the exploratory outcomes, the **index date/start of follow-up** and **exit date/end of follow-up** for MCM will be defined as in Section 9.3.2 MCM will be classified also by body system organ class according to the EUROCAT categories Guide 1.5 (section 3.3 in EUROCAT Subgroups of congenital anomalies) (41).

The full list of ICD-10 codes for MCM of interest can be found in Table 22.

Adverse outcomes related to infant growth up to 1 year of age

For the adverse outcomes related to infant growth, the **index date/start of follow-up**, included in the enrolment, will be defined as birth date from which the offspring will be followed up for the outcome of interest. The **exit date/end of follow-up** will be defined as the end of the study period, death, emigration (where available), loss to follow-up (disenrollment/de-registering), reaching the age of 1 year or date of first diagnosis of the outcome at study, whichever is the soonest.

Infant growth up to one year of age:

- Length (any time point during the first year of life – as available)
- Weight (any time point during the first year of life – as available)
- Head circumference (any time point during the first year of life – as available)

Adverse outcome related to growth up to one year of age will be a dichotomous variable defined as a composite outcome based on the presence of at least one of the following conditions: abnormal head circumference growth, stunting, or wasting. The period of assessment will be during the first year of life and the outcome will be assessed whenever anthropometric measurements are

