available. The offspring will be classified as subnormal growth if meeting at least one of the recommended WHO cut off values below at any time during the first year of life (119):

- <-2 SD z-score (equivalent to 2.3rd percentile) of head circumference-for-age based in the WHO 2006 growth charts.
- <-2 SD z-score (equivalent to 2.3rd percentile) of length-for-age to define stunting based in the WHO 2006 growth charts.
- <-2 SD z-score (equivalent to 2.3rd percentile) of weight-for-length to define wasting, based in the WHO 2006 growth charts (119).

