In DAPI, all study outcomes of interest are available or partially available (Table 16), as well as maternal characteristics, other baseline characteristics and covariates (Table 17).

Table 8: Summary of data sources and countries for this study

Country	Start of data availability	Coverage	Number of pregnancies in women with moderate to severe SLE per year ¹	Data lag (months)	Availability of exposure		Availability of outcomes				Rationale for the decision
					Anifrolumab ²	SOC	CM ³	Adverse pregnancy outcomes ⁴	Adverse birth outcomes ⁵	Infant growth outcome	
Denmark (National Registers)	Between 1970 and 2018 ⁶	100%	20	2-13	Available	Available	Available	Available	Available	Partial: - Length and weight are captured in the Children Database - No data on development available except for specific diagnoses	- Ability to capture anifrolumab exposure and primary outcomes
Finland (National Registers)	Between 1961 and 2019 ⁶	100%	16	1-24	Available	Available	Available	Partial: - Infections requiring hospitalisation during pregnancy	Available	Partial: - Height and weight might be available from HILMO and AvoHILMO	- Ability to capture anifrolumab exposure and primary outcomes
France (SNDS)	2008 (DCIR) 2006 (PMSI)	98.9%	263	12	Partial: - Only pen formulation of Belimumab delivered in retail pharmacies are captured. - Only hospital administered drugs listed as high-cost drugs are captured	Partial: - Vocosporin and mepacrine not available - Only hospital administered drugs listed as high-cost drugs are captured	Available	Partial: - Spontaneous abortion - Elective termination of pregnancy	Available	Partial: - Data on infant development is not available	- Ability to capture anifrolumab exposure (if included in the list of high-cost drugs) and primary outcomes ⁷
Germany (RHEKISS)	2015	NA ⁸	25	No	Available	Available	Available	Available	Available	Available	- Ability to capture anifrolumab exposure and primary outcomes

Country	Start of data availability	Coverage	Number of pregnancies in women with moderate to severe SLE per year ¹	Data lag (months)	Availability of exposure		Availability of outcomes				Rationale for the decision
					Anifrolumab ²	SOC	CM ³	Adverse pregnancy outcomes ⁴	Adverse birth outcomes ⁵	Infant growth outcome	
USA (Carelon Research)	2006	7% ⁹	225	3	Available	Available	Available	Available	Available	Available	- Ability to capture anifrolumab exposure and primary outcomes - Number of pregnancies captured

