² There is no direct variable to determine hospitalisations due to infection. If an ICD-10 code for infection was used as the primary reason for health care visit, then it is captured in the national registers.

³ May be extracted from medical records for a subset of patients.

⁴ High completeness for weight and length/height (with dates) in the Children’s Database, but number and frequency of measurements are unknown.

⁵ Hospital visits with a linked ICD-10 code are available. Height and weight might be available from HILMO and AvoHILMO.

⁶ The database is used for planning and funding purposes and is subject to coding quality control.

Table 17: Availability of maternal characteristics, other baseline characteristics and covariates

Databases/Countries	USA		Denmark	Finland	France	Germany
	Carelon Research	DAPI	National Registers	National Registers	SNDS	RHEKISS
Date at first SLE diagnosis	Partial ¹	Yes	Yes	Yes	Yes	Yes (year)
Age at conception (LMP2)	No ²	Yes	Yes	Partial ³	Yes	Yes
Socioeconomic status at conception	No	Not provided	Yes	No	Yes (via proxy)	No
Ethnicity	No	Yes	No	No	No	No
Pre-pregnancy BMI	Partial ^{1,4}	Yes	Yes ⁵	Yes ⁵	No	Yes
Smoking (during pregnancy)	Yes	Yes	Yes	Yes	No	Yes
Alcohol and Substance abuse (during pregnancy)	Yes	Yes	Yes	Yes	No	Yes
Pre-pregnancy diabetes	Yes	Yes	Yes	Yes	Yes	Yes
Gestational diabetes	Yes	Yes	Yes	Yes	Yes	Yes
Pre-eclampsia	Partial ¹	Not provided	Yes	Partial ⁶	Yes	Yes
Previous spontaneous abortions	Partial ¹	Not provided	Partial ⁷	Partial ⁸	Partial ⁹	Yes
Previous stillbirths	Partial	Not provided	Yes	Yes ⁸	Yes	Yes
Previous elective terminations of pregnancies	Partial ¹	Not provided	Yes	Yes	Partial ⁹	Yes
Previous preterm births	Partial ¹	Not provided	Yes	Yes	Yes	Yes
Previous small for gestational age births	Partial ¹	Not provided	Yes	Yes	Yes	Yes
Laboratory results and date of testing ¹⁰	Partial	Not provided	Yes	Yes	No	Yes
Number of healthcare visits six months before LMP2 and during pregnancy ¹¹	Yes	Yes	Yes	Yes ¹²	Yes	Partial ¹³

Abbreviations used in the table: LMP2, Last menstrual period plus 2 weeks; SLE, Systemic lupus erythematosus; UK, United Kingdom; USA, United States of America

¹ These data are available through medical claims but may be incomplete if diagnosis occurred prior to entry into an Anthem health plan.

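### Objective 12 divides infant-growth outcomes by all live offspring, although only a measured infant can have the outcome, so unmeasured infants count as growing normally

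*Protocol*

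**What the plan says.** **Outcome (Section 9.3.2).** Length, weight and head circumference are taken at any time point in the first year, as available. The three components are stunting, wasting and poor growth of the head circumference. The adverse growth outcome "will be a dichotomous variable defined as a composite outcome based on the presence of at least one of the following conditions". The text adds that "the outcome will be assessed whenever anthropometric measurements are" available, and that "The offspring will be classified as subnormal growth if meeting at least one of the recommended WHO cut off values below at any time" in the first year. There is no category for an infant who was not assessed.

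**Cohort (Table 5).** The infant cohort takes linked live offspring and excludes adopted children and births before 37 weeks. No criterion asks for a growth measurement.

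**Risk (Section 9.7.4, Objective 12).** The crude risk in each exposure group is "calculated as the total number of adverse outcomes related to infant growth divided by the total number of live offspring". The adjusted risk follows propensity score adjustment.

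**Availability (Tables 8 and 16).** Carelon Research and RHEKISS are listed as available. The other four sources are marked partial:
- DAPI: "May be extracted from medical records for a subset of patients".
- Denmark: "Length and weight are captured in the Children Database". A note to Table 16 reports high completeness for dated weight and length, with the number and frequency of measurements unknown. Head circumference is not listed there.
- Finland: height and weight might be available from two care registers.
- France: the detail given in Table 8 is that infant development data are not available.

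**The concern.** The numerator and denominator come from different groups of infants. Only infants with a usable measurement can enter the numerator, while every live infant in the cohort enters the denominator. An unmeasured infant adds one to the denominator, cannot add to the numerator, and so counts as normal growth.

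In a safety study this error leans towards reassurance, because missing data lower the reported risk. Objectives 12a and 12b place the exposed and unexposed risks side by side. A difference in how often the two groups are measured would look like a difference in growth, and a real difference could be hidden. Risks from sources with different measurement coverage would not be comparable.

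**Working it through.** The protocol states no expected risk, sample size or power for Objective 12, so there is no figure to reproduce. The check is algebra plus illustration.

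**Definitions.** N = live offspring in an exposure group of the infant cohort. M = those with a usable measurement, and m = M/N. C = infants below a cut-off, all of whom are among the M. r = C/M = risk among measured infants. u = risk among unmeasured infants, which is not observed.

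**Stated formula.** C/N = (M/N) × (C/M) = m × r.

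**Risk in the whole cohort.** m × r + (1 − m) × u. The stated formula equals this only if m = 1 or u = 0, that is, only if everyone is measured or no unmeasured infant has the outcome. Otherwise it is too low.

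**Illustration 1: the protocol's own cut-off.** Section 9.3.2 describes −2 SD as "equivalent to 2.3rd percentile) of length-for-age to define stunting". P(z < −2) = 2.28%. For any of three components, each measured once and assumed independent, the risk is 1 − (1 − 0.02275)³ = 6.67%.

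| Share measured (assumed) | One component | Any of three | r = 10% (assumed) |
|---|---|---|---|
| 1.00 | 2.28% | 6.67% | 10% |
| 0.50 | 1.14% | 3.34% | 5% |
| 0.25 | 0.57% | 1.67% | 2.5% |

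Dividing by M instead returns the top row for every m above 0.

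**Illustration 2: different shares by exposure group.** Take r = 10% in both groups.
- 60% of exposed and 40% of unexposed measured: 0.10 × 0.60 = 6% against 0.10 × 0.40 = 4%, a ratio of 1.5 with no true difference.
- Shares reversed: 4% against 6%, a ratio of 0.67.

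**Illustration 3: a missing component.** If a source lacks head circumference, only two components can be met. On the same independence assumption, full measurement of those two gives 1 − (1 − 0.02275)² = 4.50%, against 6.67% where all three are held. The composite therefore differs between sources even without unmeasured infants.

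**Adjusted risk.** The propensity score in Section 9.7.1 models exposure from maternal factors and year of conception. It does not model whether an infant was measured, so the adjusted risk inherits the denominator.

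**The case against.** The strongest reply is that the missing-data rule already covers this. Section 9.7 says imputation, complete-case analysis or a missing-value indicator will be considered, with details in the SAP, and a complete-case analysis is close to the repair proposed here. Section 9.9 concedes that first-year growth may not be available in every database and promises to report missing information. No sentence says outright that an unmeasured infant is a non-event. This stands in part: the SAP could restrict the analysis to measured infants. But the clause is general and only promises consideration, whereas Section 9.7.4 names an explicit denominator. The item is stated and stated badly; it is not left open.

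Three stronger readings are tempting and are not supported:
- *That some sources hold no growth measurements.* No source is listed as having none. Denmark reports high completeness for weight and length. The Finnish Medical Birth Register records weight, length and head circumference at or around birth (Section 9.4.1.2, Table 15). The French entry concerns development and leaves anthropometry unclear.
- *That the reported risk mostly reflects how often infants are measured, or that exposed infants are measured more.* No measurement share is given for any source or group.
- *That a risk ratio is biased.* Section 9.7.1 and the abstract plan none for Objective 12, and the meta-analysis covers only the primary objectives.

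It is also fair to say that dividing by measured infants is not bias-free. In a medical-record subset or a care-visit register, measurement may follow a clinical worry, and the risk among measured infants may then exceed that of the cohort.

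**Conclusion.** The point holds in a limited form. As written, the Objective 12 formula counts unmeasured infants as non-events, and each group's risk equals the risk among measured infants multiplied by the share measured. This follows from Sections 9.3.2 and 9.7.4 and Table 5 alone. That measurement will be incomplete somewhere rests on the partial markings for DAPI, Denmark, Finland and France.

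The size is unknown. The 10% risk, every measurement share, any difference by exposure group and the independence of the components are assumptions used for illustration. The direction within a group does not depend on them: any share below 1 puts the stated figure below the risk among measured infants. Distortion between the groups arises only if their shares differ, and the documents do not say whether they do.

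The consequence is confined to one exploratory, descriptive objective. No primary or secondary result is affected.

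**What to change.** Change the wording for Objective 12 in Section 9.7.4:
- Calculate each component's risk among infants with at least one post-birth measurement in year 1 that allows that component to be scored. The post-birth condition is needed because the abstract starts assessment at birth, so a birth measurement alone would otherwise qualify an infant who was never measured again.
- Give the composite among infants assessable for it, and state for each source which components contribute.
- Report the number and share measured by exposure group and source.
- Report no risk for a source that proves to hold no usable measurements.

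The cost is smaller denominators and possibly no estimate in some sources. Measured infants may be a selected group; this should be stated as a limitation in Section 9.9, and the reported shares let a reader judge it. No additional data collection is needed.
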